9.7.4 Subgroup Analyses

The SAP will include details for subgroup analysis.

9.7.5 Adjustment for Multiple Comparisons

Multiplicity of the primary efficacy analyses is controlled by using a conditional sequence of hypotheses. The study will be considered to demonstrate statistical significance if the primary analysis has a resulting p-value less than 0.05. No other adjustment for multiplicity is required.

9.8 SAFETY ANALYSIS

The SAF is used for safety analysis. Adverse events, ECGs, vital signs and safety laboratory data will be reviewed and summarized on an ongoing basis during the trial to evaluate the safety of participants.

9.8.1 Safety Variables of Analysis

9.8.1.1 Adverse Events

Definitions:

- A *treatment-emergent adverse event* (TEAE) is an event that is observed or reported after administration of study medication that was not present prior to study medication administration or an event that represents the exacerbation of a pre-existing event.
- An *adverse withdrawal* is a subject who withdrew from the study due to an adverse event.
- A *serious adverse event* (SAE) is an AE that is classified as serious according to the criteria specified in the study protocol.

Adverse events variables of analysis include:

- Proportions of subjects with TEAEs by Preferred Term and decreasing frequency of TEAE
- Proportions of subjects with TEAEs by System Organ Class and Preferred Term
- Proportions of subjects with adverse withdrawals

9.8.1.2 Vital Signs

Vitals signs measures of blood pressure and pulse will include the following variables of analysis:

- Mean values and mean changes of values from Baseline to Visit
- Proportions of subjects with abnormal values or changes in vital signs measures of potential clinical concern.
- Proportions of subjects with AEs related to vital signs

9.8.1.3 Clinical Laboratory

Clinical Laboratory hematology and clinical chemistry variables of analysis include:

- Proportions of subjects with TEAVs (shifts from normal status to abnormal status)
- Proportions of subjects meeting DILI criteria per FDA guidance, *Guidance for Industry “Drug-induced liver injury: premarketing clinical evaluation”* (CDER, CBER, July 2009)
- Means and mean changes from Baseline to Visit
- Proportions of subjects with new (post Baseline) values (Clinical laboratory-related AEs) or changes in laboratory values of potential clinical concern

9.8.1.4 Electrocardiography

Electrocardiography variables of analyses will include:

- Proportion of subjects with Corrections to QT intervals will be made by Fridericia's method. Categorical analysis will be done consistent with ICH E14, “Clinical evaluation of QT/QTc interval prolongation and proarrhythmic potential for non-antiarrhythmic drugs” (October 2005).

9.8.2 Statistical Methodology for Safety Analysis

Adverse events will be coded using MedDRA Version 21.0 or above. Adverse event coding will be done to the lowest level term (LLT). All treated patients will be included in the assessment of safety. Adverse events will be summarized by MedDRA System Organ Class and Preferred Terms. Separate tabulations will be produced for related AEs (those considered by the Investigator as drug related), SAEs, discontinuations due to AEs, and severe events.

Vital signs, ECG results, and laboratory data will be tabulated for changes over time on study. In addition, TEAV and significant findings will be summarized.

For each post-Baseline assessment, descriptive statistics are provided for the assessment value and the change from Baseline to the assessment.

9.9 PHARMACODYNAMIC DATA

All participants with at least one dose of study medication will be included in the pharmacodynamic analyses, as appropriate. For individual endpoints, participants must have at least 1 post-dose pharmacodynamic measurement for the given endpoint. For change from Baseline, participants must also have a Baseline value.

Plasma A β (total, 1-40 and 1-42) concentration and cerebral brain volume (hippocampus and whole brain, ventricular) versus time will be tabulated and mean concentration or brain volume versus time will be plotted for each treatment group. Descriptive statistics for raw and change from baseline values will be generated, as appropriate. Maximum and average change from Baseline values will be calculated by treatment group.

The statistical methods will be described in the SAP.

9.10 PHARMACOKINETIC DATA

Data resulting from blood sampling for trough concentrations of azeliragon will be collected and summarized descriptively. Concentration-driven analysis of the relationship between azeliragon (and potentially metabolite concentrations) and

efficacy/safety may be performed. The statistical methods will be described in the SAP.

9.11 QUESTIONNAIRES

Questionnaires include cognitive assessment, functional assessments, behavioral assessments, and assessments of quality of life. Questionnaires in this study will be scored according to the published guidelines provided in validation and documentation for the instruments by the developers. The statistical methods will be described in the SAP.

9.12 HANDLING MISSING DATA

Data are considered to be “on-treatment” if the assessment of collection follows the first administration of study medication and if the assessment occurs within 45 days following the final administration of study medication, justified based on the long half-life of this drug.

In general, for primary efficacy analysis and for safety analysis, missing data will not be imputed. Dates with missing fields will not have days imputed.

In accordance with the recommendations of the report from the National Academy of Science (NAS) panel “*The Prevention and Treatment of Missing Data in Clinical Trials*,” (National Research Council, 2010), sensitivity analyses will be done to ensure that study conclusions are robust against missing data. Last observation carried forward (LOCF) and baseline observation carried forward (BOCF) methods will be used as appropriate in sensitivity analysis. Missing data types will be examined, and statistical methodologies for appropriate sensitivity analyses will be finalized during blind data review as patterns emerge as the study progresses. Primary methodologies following the ITT principle are not subject to change.

Details of methodologies identifying data as missing at random (MAR) or not missing at random (NMAR) will be addressed in the SAP. Statistical methods for addressing MAR and NMAR will be described in the SAP.

9.13 DATA MONITORING COMMITTEE

An external Independent Data Monitoring Committee (IDMC) will be responsible for the review of all available safety data at their regularly scheduled meetings during the trial.

The IDMC will consist of at least 3 members, including a neurologist who has experience in the treatment of individuals with AD and a senior statistician. Ad hoc members (e.g., experts on RAGE mechanisms or a cardiovascular physician) will be available for consultation by the IDMC upon request.

The IDMC will initially be provided with data displays in accordance with the IDMC charter.

Blinded summary IDMC reports will also be distributed to all participating sites for local IRB/REB submission, where applicable. The IDMC will meet in person or by conference call on a quarterly basis. The IDMC charter will specify these and other operational aspects of the IDMC structure, processes and study stopping rules.

9.14 INTERIM ANALYSIS

Except for the ongoing, blinded medical monitoring of accruing data and except for the ongoing review by the IDMC, no interim analysis is planned for Part 1 or Part 2.

Although this study has an adaptive design, and sample size re-estimation for Part 2 of the study is a potential feature for revaluation, the analysis of Part 1 to be used for the re-estimation is to be done as a final analysis following the database lock, hence, the analysis will not be an interim analysis. It is acknowledged that a blinded analysis is considered an interim analysis in accordance with the draft guidance from the FDA on adaptive designs, and no interim analysis is intended for this study.

As a conservative measure, an alpha adjustment is applied to accommodate analyses by the IDMC because the safety evaluation will include review of ADAS-cog14 data from the safety perspective. Alpha = 0.0001 is divided among no more than 4 interim analyses in the 100-subject, 6-month trial (for an alpha adjustment of 0.0001, which is considered to be negligible, so alpha=0.05 is available for the final analysis); for Part 2, alpha = 0.0001 is apportioned to each of no more than 10 analyses by the

IDMC that includes review of ADAS-cog14 data, blinded unless there is a data-driven need expressed by the IDMC to be unblinded.

With the possible exception of the IDMC, no unblinding is planned in this study for any reason other than emergency unblinding for medical imperatives.

It is emphasized that there is no interim analysis in this study for efficacy. The interim analyses described in this section refer to the analyses done by the IDMC for safety monitoring only.

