Exploratory analysis of concentration-driven assessment of PK/PD effects included the quantile cuts described above and also iterative analysis focused on identification of a concentration range that was associated with optimal effectiveness for efficacy measures (primary and secondary measures). The iterative analysis included construction of groups with minimum trough concentrations ranging from 1 to 20 ng/ml. Within these groups, ranges were derived using optimization techniques to identify concentration groups that maximized efficacy. The results of the exploratory PK/PD analysis concluded that the optimal trough concentration range was 8-15 ng/ml over the 18-month period.

Based on the considerations outlined above, a 5 mg/day dose was selected. Doses below 5 mg/day and between 5 mg/day and 20 mg/day were considered. Doses below 5 mg/day are expected to provide non-efficacious concentrations. Doses above 5 mg/day (ex: 10 mg/day) are not expected to provide significantly improved efficacy relative to the potential for achieving concentrations associated with acute, reversible cognitive worsening.

The effect of food on the pharmacokinetics of azeliragon was evaluated in the TTP488-105 study. There was an approximately 20% reduction in exposure (C_{max} , AUC_{0-last} , and AUC_{0-72}) following administration of a single 5 mg dose of azeliragon following a standard FDA high fat breakfast compared to dosing in the fasted state. Fed subjects experienced a greater lag time for absorption as compared to fasted subjects (median T_{lag} of 4 hours versus 1 hour post-dosing, respectively); however, the median T_{max} was the same between treatment groups (16 hours post-dosing). Therefore, azeliragon may be administered without regard to food.

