1.7 Early Stopping, Data Monitoring, and Interim Analysis

There will be no interim analyses.

An adjustment for alpha is included in the original protocol, as a conservative measure to accommodate unblinded evaluations by the independent data monitoring committee (IDMC). The alpha adjustment is applied to accommodate up to 10 analyses by the IDMC because the safety evaluation will include review of ADAS-Cog data from the safety perspective. Alpha = 0.0001 is apportioned to each of no more than 10 analyses by the IDMC that includes review of ADAS-Cog data.

There will be two database locks: one for the double-blind treatment period, and one for the follow-up period. Final analysis will be performed on the interim database after all subjects complete the treatment period (Month 6 or Early Termination) and all Treatment Period data is locked. The final database lock will occur after all Follow-up Visits are complete.

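### Protocol 9.14 makes the IDMC's ADAS-cog14 safety review blinded by default, which weakens detection of cognitive harm, and the SAP differs from it on blinding, number of looks and alpha for Part 1.

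*Protocol*

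**What the plan says.** Protocol 9.14 plans no interim efficacy analysis. It deducts a little alpha because the IDMC will look at ADAS-cog14 for safety. For Part 1, "Alpha = 0.0001 is divided among no more than 4 interim analyses in the 100-subject, 6-month trial". Part 2 has up to 10 such analyses at 0.0001 each, "blinded unless there is a data-driven need expressed by the IDMC to be unblinded". The same section then says that, the IDMC possibly excepted, only medical emergencies justify unblinding.

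Protocol 9.13 gives the IDMC all available safety data at its regular meetings: "The IDMC will meet in person or by conference call on a quarterly basis". Data displays, processes and stopping rules are left to the charter, which is not among the documents.

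SAP 1.7, in a plan that covers Part 1 only, describes the protocol's deduction differently. It is there "to accommodate unblinded evaluations by the independent data monitoring committee (IDMC"), and "Alpha = 0.0001 is apportioned to each of no more than 10 analyses by the IDMC that includes review of ADAS-Cog data". SAP 6.6 sets the primary alpha at 0.0499; SAP 6.4 sets it at 0.049.

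On the clinical background, Protocol 1.1.4 explains why doses above 5 mg/day were not chosen, citing the "potential for achieving concentrations associated with acute, reversible cognitive worsening".

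**The concern.** The sponsor treats ADAS-cog14 as safety data and pays alpha for the IDMC to see it. Under Protocol 6.4 the IDMC may advise that a subject stop dosing, may pause dosing or enrolment, and may end the study. To judge a cognitive harm it needs to know whether one arm is declining faster than the other. A review without arms shows only the average of the two, in a disease where both decline. The condition for unblinding is close to circular for this outcome, because the need must appear in data that hide the contrast of interest.

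Separately, an IDMC or reporting statistician who follows both documents cannot tell how many ADAS-cog looks are allowed in Part 1, whether they are by arm, or which alpha remains at the end.

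**Working it through.** **1. Alpha.** The protocol's own figures reproduce.
- Part 1, protocol: 4 looks share 0.0001, so 0.05 − 0.0001 = 0.0499, as in Protocol 9.7.2 (which then treats it as 0.05).
- Part 2, protocol: 10 × 0.0001 = 0.001, so 0.05 − 0.001 = 0.049, as in Protocol 9.7.2.
- Part 1, SAP 1.7: 10 × 0.0001 = 0.001, leaving 0.049. That is the figure in SAP 6.4. SAP 6.6 has 0.0499, which fits only the protocol's 4-look plan.

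So the SAP carries two final alphas for one primary test, each matching a different look plan.

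**2. What an arm comparison can see.** Inputs from Protocol 9.2: Part 1 SD 4, difference 2.9, 41 per arm; Part 2 SD 7.5, difference 4.5, 60 per arm. The standard error is SD × √(2/n).
- Part 1: 4 × √(2/41) = 0.883; 2.9 / 0.883 = 3.3 SE; t-test power 90.0% at 0.05.
- Part 2: 7.5 × √(2/60) = 1.369; 4.5 / 1.369 = 3.3 SE; t-test power 90.2% at 0.049.

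Both agree with the planned power of at least 90%. A harm of the same size as the planned benefit is equally visible by arm at full sample size.

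**3. What pooled data can see.** With 1:1 allocation, a harm of D in one arm moves the pooled mean by D/2. Protocol 1.1.3 gives placebo declines of 3, 6 and 10 points in 18 months from different sources, a spread of 10 − 3 = 7. Month 6 values assume linear decline: 7/3 = 2.3.

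| | Harm D | Pooled shift D/2 | Spread in placebo decline | Spread / shift |
|---|---|---|---|---|
| Part 1, Month 6 | 2.9 | 1.45 | 2.3 | 1.6 |
| Part 2, Month 18 | 4.5 | 2.25 | 7 | 3.1 |

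In both parts the shift is smaller than the uncertainty about natural decline, so a pooled mean cannot separate harm from a faster-declining population.

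The pooled spread of scores helps little. Pooled SD = √(SD² + D²/4):
- Part 1: √(16 + 2.10) = 4.25, against 4.00.
- Part 2: √(56.25 + 5.06) = 7.83, against 7.50.

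A one-sided 5% test for this increase, with the true SD taken as known and all 82 or 120 subjects assessed, has about 21% and 17% power.

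**4. Look caps against quarterly meetings.** A cap of k looks covers 3k months. Counting to the last subject's last dose, it falls short only if accrual exceeds 3k minus the treatment period.

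| | Cap | Months covered | Treatment (months) | Short if accrual exceeds |
|---|---|---|---|---|
| Part 1, protocol | 4 | 12 | 6 | 6 months |
| Part 1, SAP | 10 | 30 | 6 | 24 months |
| Part 2, protocol | 10 | 30 | 18 | 12 months |

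Counting the 3-month off-drug follow-up as well, the limits become 3, 21 and 9 months. No accrual period is given in either document.

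**The case against.** The strongest reply is that the IDMC is not confined to a pooled mean. It sees all safety data. Adverse events, withdrawals or abrupt changes in single subjects could each supply the need to unblind; the IDMC itself expresses that need, and no sponsor consent is mentioned. The charter may already provide closed reports by arm. This stands. A reader might infer that the IDMC cannot detect cognitive harm at all; the documents do not support that.

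For Part 1, the SAP says it supersedes the protocol's statistical section, so its unblinded reviews and 10 looks could be said to govern. That has force on blinding, since the blinded wording sits in the Part 2 clause. It does not settle the number of looks: SAP 1.7 presents its figures as those of the protocol, SAP 1.9 does not list a change, and SAP 6.6 keeps the alpha of the 4-look plan. The SAP does not cover Part 2, where blinded by default is the only rule in the documents.

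Three further inferences go too far.
- That the caps are lower than the number of meetings: this depends on accrual. SAP 1.4 reports slow enrolment and 43 subjects of 100, but no duration.
- That cognitive worsening is a stated risk of the study dose: Protocol 1.1.4 ties it to concentrations that higher doses might reach.
- That the alpha is wasted: the protocol calls the deduction conservative, and it covers the possibility of unblinding.

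The 90% power is also for a full dataset. Assuming half of the 43 enrolled subjects assessed (10 and 11) and SD 3.4, the ADAS-cog11 estimate in SAP 1.6, SE = 3.4 × √(1/10 + 1/11) = 1.49, and 2.9 points is 1.95 SE. An early look by arm is therefore modest evidence, but it addresses the right contrast.

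Lastly, SAP 6.4 refers to two primary endpoints and to an A-study and B-study, neither of which is the Part 1 design. Its 0.049 may be carried-over text. That would explain the conflict without removing it.

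**Conclusion.** The point holds in a limited form. Blinded-by-default review weakens the IDMC's view of between-arm cognitive harm. A harm equal to the design difference moves the pooled mean by 2.25 points in Part 2 and 1.45 in Part 1, inside spreads of 7 and about 2.3 points in the protocol's own placebo declines. This rests on 1:1 allocation, on harm of that size and, for Part 1, on linear decline. The weakness matters most in Part 2, planned for 200 subjects over 18 months.

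The conflict for Part 1 needs no such assumption: at most 4 looks sharing 0.0001 against up to 10 at 0.0001 each, with 0.0499 and 0.049 both given as the final alpha in the SAP. The SAP also calls the reviews unblinded, while the only blinding rule in the protocol is blinded by default. The 0.0009 gap in alpha is small, but a p-value between the two figures would be read both ways.

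A shortfall of looks against quarterly meetings is possible, not shown. Neither document says what happens to ADAS-cog14 review if the cap is reached.

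**What to change.** In Protocol 9.14, the SAP and the charter:
- State one blinding rule and one maximum number of ADAS-cog14 looks for each part, with the matching alpha. For Part 1 that is 0.0499 with the protocol's looks or 0.049 with the SAP's, used identically in SAP 1.7, 6.4 and 6.6.
- Give the IDMC closed ADAS-cog14 summaries by arm at each scheduled review, coded A and B with codes on request. Keep the sponsor and sites blinded.
- State that the look count is for alpha accounting only, and that reaching it does not remove ADAS-cog14 from safety review.

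The cost is mainly wording. An alpha deduction is already planned and there is no efficacy stopping. The small downside is that someone outside the sponsor's blinded team must prepare the closed reports, a role that the unblinded looks already permitted would need anyway. Part 1 enrolment has stopped, so there the gain is a single alpha and a clear record of the looks held; the by-arm reports mainly serve Part 2.

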9.15 DATA MANAGEMENT CONSIDERATIONS

This study will utilize electronic data capture (EDC) for data capture. The database lock will occur when each Part of the study is declared closed, when all subjects have completed the study part (last visit of the last subject on-study).

10.0 QUALITY CONTROL / MONITORING OF THE STUDY

During study conduct, the Sponsor or its designee will conduct periodic monitoring visits to ensure that the protocol and GCPs are being followed. The monitors may review source documents to confirm that the data recorded on CRFs is accurate. Additionally, the study site may be subject to quality assurance audits performed by the Sponsor, and/or to inspection by the IRB/REB or regulatory authorities.

11.0 DATA HANDLING AND RECORD KEEPING

11.1 CASE REPORT FORMS/ELECTRONIC DATA RECORD

This study will utilize electronic data capture (EDC) for the data record serving as the “Case Report Form (CRF)”. All required study information must be recorded on the appropriate CRF screens/forms using the eCRF Completion Guidelines for the study. Quality control measures will progress final data management activities from last-patient-last-visit to database lock, then unblinding, final analysis, and final reported for each part of the study. The database lock will occur when the study is declared closed, when all participants have completed the study (last visit of the last subject on-study) and the data are fully monitored with all queries resolved.

The PI is responsible for ensuring that the data collected is collected/reported in a timely manner and is accurate, complete and legible. Data will be verified within the eCRF by the Study Site and the Study Monitor before being exported. Any changes made during verification will be documented with a full audit trail.

Any missing or inconsistent data entries will be referred back to the PI or designee, using a data query form, and documented for each individual study participant before eCRFs are frozen and signed by the PI. From that point forward, the database will be protected from changes (database lock).

11.2 RECORD RETENTION

For sites in the United States, the PI/Study Site must retain all study records, including regulatory documents and individual study participant records, for a period of 2 years following the date a marketing application is approved for the drug, for the indication for which it is being investigated; or, if no application is to be filed, or if the application is not approved, until 2 years after the investigation is discontinued, and the FDA is notified or longer if requested by Sponsor (per 21 CFR 312.62).

For sites in Canada, the PI/Study Site must retain all study records, including regulatory documents and individual study participant records, for a period of 25 years after the date of completion of trial (per FDR C.05.012).

If the investigator becomes unable for any reason to continue to retain study records for the required period (e.g., retirement, relocation, closure of facility), the Sponsor should be prospectively notified. The study records must be transferred to a designee acceptable to vTv Therapeutics, such as another investigator, another institution, or to vTv Therapeutics. vTv Therapeutics needs to be notified and approval obtained before records may be transferred off site.

